8.5 SPONSOR	9
8.6 FUNDING	9
8.7 AUDITS AND INSPECTIONS	9
9. STUDY MANAGEMENT	9
10. PUBLICATION POLICY	9
11. REFERENCES	10
APPENDIX 1: Figures	11
APPENDIX 2: Summary of investigations and assessments	12

STUDY SUMMARY

TITLE: What is the impact of a modified Roux-en-Y-gastric bypass (RYGB) operation on people with type 2 diabetes mellitus? The LONG LIMB-2 double-blinded randomised controlled clinical trial

DESIGN: Double-blind randomised controlled clinical trial

AIMS: To investigate if a “modified” RYGB procedure is equally safe but superior to “standard” RYGB in improving glycaemic control in patients with type 2 diabetes mellitus (T2DM) and obesity.

OUTCOME MEASURES: Change in glycated haemoglobin (HbA1C) from baseline.

POPULATION: Men and women with T2DM and obesity

ELIGIBILITY: Diagnosis of T2DM, body mass index (BMI) $>30 \text{ kg/m}^2$, aged between 18 – 65 years, eligible for metabolic/bariatric surgery as per NICE CG189

DURATION: 3 years

1.1 BACKGROUND AND RATIONALE

The profound improvements in glucose control after RYGB have unexpectedly led to the recognition of the intestine as an organ with a major impact on glucose regulation. Thus, surgeons have experimented with different intestinal limb lengths in an attempt to enhance the clinical effect of RYGB on glucose control. However, the optimal length of each of these limbs remains controversial with substantial variation in practice. The matter is complicated further by the variability in the total length of the human small intestine (range of 3.5–10.5 metres) [8].

The anatomical rearrangements of RYGB result in three intestinal segments or “limbs”: the “alimentary limb” through which food enters through the gastric pouch to the small intestine, the “biliopancreatic limb” which includes the bypassed segments of duodenum and proximal jejunum through which the biliopancreatic secretions flow, and the “common limb” (or channel) in which the food and biliopancreatic secretions mix (Figure 1A). More recently, our clinical and mechanistic data, together with other clinical trials and animal experiments [9-11] have shifted the focus from the biliopancreatic limb to the lengths of the alimentary and common limbs. The evidence supports the hypothesis that a “modified” RYGB with a long alimentary limb and short common limb may be the optimal design for glycaemic control (Figure 1C).

It should be noted that this “modified” RYGB (Figure 1C) is not new and indeed currently performed around the world. There is no signal that it is associated with higher morbidity compared to the standard RYGB [12]. However, a formal comparison between the “modified” and “standard” RYGB with glycaemic control as the primary outcome has never taken place.

Hypothesis: A “modified” RYGB procedure with a long alimentary and short common limb (40:60) is equally safe but superior to the “standard” RYGB with a short alimentary and long common limb (20:80) for glycaemic control in patients with T2DM and obesity.

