2. STUDY OBJECTIVES

To perform a double-blind RCT to compare safety and efficacy of “modified” RYGB vs. “standard” RYGB in improving glycaemic control in patients with T2DM and obesity. Secondary objectives from baseline to 12 months post operatively are changes in:

- Rate of remissions of T2DM
- Number of glucose-lowering medications
- Body weight
- Arterial blood pressure
- Lipid profile
- Adverse events (including surgical complications, hypoglycaemia and micronutrient deficiencies)

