3.1 STUDY OUTCOME MEASURES

Primary outcomes

- Change in HbA1C from baseline to 12 months

Secondary outcomes

Change from baseline to 12 months for:

- Rate of remission of T2DM
- Number of glucose-lowering medications
- Body weight
- Arterial blood pressure
- Lipid profile
- Adverse events (including surgical complications, hypoglycaemia and micronutrient deficiencies)
- Rate of intestinal absorption of ingested glucose (mechanistic study only)

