7. STATISTICS AND DATA ANALYSIS

Justification of sample size

Based on our own data from the LONG LIMB-1 trial and the most relevant RCT in the field [12] we estimated that the absolute HbA1c reduction in the standard RYGB group will be 3.0% and in the modified RYGB group 4.0%. With a standard deviation of 1.2% around both means and using a 1:2 randomisation, we will need 24 participants in the standard RYGB and 48 in the modified RYGB to have a 90% power to detect statistically significant differences between the groups at α of 0.05. We will recruit 80 patients in total to account for an approximate 10% drop-out rate based on rates in similar trials we have conducted in this field (e.g. LONG LIMB-1 trial ISRCTN15283219).

Statistical analysis plan

Analysis of the data will only take place after completion of the trial having written a statistical analysis plan and use the intention-to-treat principle. Analysis will take place by staff blinded to participant disposition. Data will be summarised using descriptive statistics. Differences between treatment groups

will be compared using regression models adjusting for the randomisation stratification variables. For binary outcomes this will be a logistic regression model and for continuous this will be a linear regression model.

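### The aim and hypothesis claim equal safety, but no safety endpoint or margin is set and the sample size rests on HbA1c alone

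*Protocol*

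**What the plan says.** The aim in the study summary is to find out whether the modified "RYGB procedure is equally safe but superior to" the standard operation in improving glycaemic control. The hypothesis in section 1.1 repeats the claim: a modified "procedure with a long alimentary and short common limb (40:60) is equally safe but superior to the" standard one. Section 2 sets the objective as "To perform a double-blind RCT to compare safety and efficacy of" the two operations.

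Section 3.1 names one primary outcome, "Change in HbA1C from baseline to 12 months". Safety is a single line among the secondary outcomes: "Adverse events (including surgical complications, hypoglycaemia and micronutrient deficiencies". No event type is singled out as the key one.

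Section 7 derives the sample size from HbA1c alone. Its assumption reads: "the absolute HbA1c reduction in the standard RYGB group will be 3.0% and in the modified RYGB group 4.0" (percent). The SD is taken as 1.2%, allocation as 1:2, power as 90% and α as 0.05. The section gives no complication rate, safety margin or target precision for safety. It describes regression comparisons between groups, descriptive summaries, and a statistical analysis plan to be written before analysis.

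**The concern.** To show that two operations are equally safe, a trial must exclude a difference that would matter. That takes an endpoint, a margin and enough patients. A test for a difference does not do this: failing to reach significance is the expected result when events are few, whether or not the operations differ.

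Half of the stated hypothesis therefore has no design behind it. The hypothesis and the basis of the sample size are fixed in the protocol, so a later analysis plan can add methods but cannot supply the missing patients. What is at stake is the safety sentence in the final report. A reader who meets a non-significant adverse event comparison next to this hypothesis may take equal safety as shown, when the data could still allow a doubling or tripling of complications.

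**Working it through.** **Inputs.** From section 7: 24 standard and 48 modified patients analysed, 80 recruited, HbA1c difference 4.0 − 3.0 = 1.0, SD 1.2, α 0.05 (taken as two-sided), power 90%. Assumed, because the protocol gives none: event rates of 2% to 40% and safety margins of 5 or 10 percentage points.

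**1. The plan's own figure.** √(1/24 + 1/48) = √0.0625 = 0.25. The standardised effect is 1.0 / (1.2 × 0.25) = 3.33, and Φ(3.33 − 1.96) gives 91.5% power (90.8% by the noncentral t). Then 72 / (1 − 0.10) = 80. The HbA1c sample size is correct.

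**2. Precision for safety.** With equal true rate p in both arms, the 95% half-width for the risk difference is 1.96 × 0.25 × √(p(1 − p)) = 0.49 × √(p(1 − p)).

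| Assumed rate | Calculation | Half-width |
|---|---|---|
| 5% | 0.49 × 0.218 | 10.7 points |
| 10% | 0.49 × 0.300 | 14.7 points |
| 20% | 0.49 × 0.400 | 19.6 points |

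The normal approximation is rough at small counts. Newcombe's interval for 2/48 against 1/24 (4.2% in each arm) runs from −16.4 to +10.4 points, which leads to the same reading.

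**3. Power to see a difference.** Fisher's exact test, two-sided 0.05, enumerated over all outcomes with 24 standard and 48 modified patients:

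| Standard | Modified | Power |
|---|---|---|
| 5% | 10% | 3% |
| 5% | 15% | 15% |
| 10% | 20% | 13% |
| 10% | 30% | 43% |
| 10% | 40% | 77% |

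**4. No events at all.** The exact two-sided 95% upper limit for 0/48 is 1 − 0.025^(1/48) = 7.4%. If all 80 recruited patients are counted, about 27 and 53, the limit for 0/53 is 1 − 0.025^(1/53) = 6.7%.

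**5. What a margin would have required.** For non-inferiority with equal true rates, one-sided 0.025 and 80% power, the standard arm needs 1.5 × p(1 − p) × (1.96 + 0.842)² / margin², and the modified arm twice that.
- 5% rate, 10-point margin: 1.5 × 0.0475 × 7.849 / 0.01 = 55.9, so 56 + 112 = 168 patients. With 24 and 48, power is 45%.
- 5% rate, 5-point margin: 1.5 × 0.0475 × 7.849 / 0.0025 = 223.7, so 224 + 448 = 672 patients. With 24 and 48, power is 15%.
- 2% rate, 10-point margin: 1.5 × 0.0196 × 7.849 / 0.01 = 23.1, so 24 + 48 = 72 patients. With 24 and 48, power is about 82%, but the margin is five times the assumed rate and the approximation is weak at such counts.

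**The case against.** **No decision rule is stated.** Nowhere does the protocol say that equal safety will be concluded from a non-significant result. Section 2 speaks only of comparing safety, section 3.1 makes adverse events secondary, and section 7 claims power for HbA1c alone. This stands: the misreading is one that the hypothesis invites, not one that the protocol prescribes. It does not rescue the hypothesis, which still asserts something the trial cannot test.

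**The trial is not blind to every difference.** A reader might infer that 24 and 48 patients yield non-significance almost whatever the truth. That is too strong: power is 43% for 10% against 30% and 77% for 10% against 40%. Nor is the trial too small for every margin, as the last case in the working shows.

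**The logistic model.** Section 7 says "For binary outcomes this will be a logistic regression model and for continuous this will be a linear regression model", and a reader might infer that the planned analysis breaks down for complications. The document does not support that. The sentence is a general rule, it suits diabetes remission, and it does not assign adverse events to that model. An arm without events is likely at a 2% rate (76% chance that at least one arm is empty), but the chance is 9% at 10% and 0.5% at 20%. The protocol gives no rates, and hypoglycaemia or micronutrient deficiencies need not be rare. Handling of sparse data properly belongs in the analysis plan.

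**Denominator.** Randomisation is intra-operative, so early complications may be seen in nearly all 80 patients. That is fair, but it changes little: 6.7% in place of 7.4% in the working's fourth step.

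**Oversight.** Section 9 provides for a Data Monitoring & Ethics Committee, and sections 3 and 4.3 keep patients with a short calculated common channel out of randomisation. Safety is attended to, but neither provision supplies a margin.

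**Conclusion.** The point holds as a mismatch between claim and design. The aim and hypothesis assert equal safety, while the protocol has no key safety endpoint, no margin and a sample size built on HbA1c only. At assumed rates of 5% to 20%, the trial can locate the risk difference only to within about 11 to 20 points either way. It would usually miss a doubling from 5% or 10%, or a tripling from 5%. Only large differences in common events are likely to show. A non-significant comparison could not carry the words *equally safe*.

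These sizes depend on the assumed event rates and on 24 and 48 patients analysed; counting all 80 does not change the conclusion. It would be wrong to infer that the trial's main result is at risk. The HbA1c calculation reproduces and the primary analysis is untouched, so the point is worth correcting but ranks below a flaw in the primary design.

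**What to change.** In the study summary and in section 1.1, replace the equal-safety claim with superiority for glycaemic control, with safety compared descriptively. In section 7, add two statements: that equal or non-inferior safety will not be concluded from a non-significant difference, and that adverse events will be reported by type and arm as counts and risk differences with 95% confidence intervals. The choice of interval and any adjusted model for sparse events can stay in the analysis plan.

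If the sponsor wishes to keep the claim, the protocol must instead name a key safety endpoint, justify a margin and show the power for it. Under most of the rates and margins shown above, that means a larger trial.

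The rewording needs no extra patients, visits or data. Its cost is a less favourable safety statement. It should be made before any results by arm are seen.

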2. STUDY OBJECTIVES

To perform a double-blind RCT to compare safety and efficacy of “modified” RYGB vs. “standard” RYGB in improving glycaemic control in patients with T2DM and obesity. Secondary objectives from baseline to 12 months post operatively are changes in:

- Rate of remissions of T2DM
- Number of glucose-lowering medications
- Body weight
- Arterial blood pressure
- Lipid profile
- Adverse events (including surgical complications, hypoglycaemia and micronutrient deficiencies)

3. STUDY DESIGN

In the LONG LIMB-2 prospective double-blinded RCT we propose to recruit 80 patients with T2DM and obesity who are eligible for metabolic surgery based on NICE guidance 189 who are on the waiting list for bariatric surgery at Imperial College Healthcare NHS Trust, North Bristol NHS Trust, King’s College Hospital NHS Foundation Trust and The Whittington Hospital NHS Trust obesity service. Randomisation will take place intra-operatively. The surgeon will measure total intestinal length and decide if the patient can be randomised intraoperatively (only patients with a calculated common channel length of >2.5m will be randomised) and if so will contact the randomiser who will make the allocation at the time to either:

- A “standard” RYGB or
- A “modified” RYGB

The randomisation ratio will be 1:2 i.e. 24 participants for standard RYGB and 48 for modified RYGB.

3.1 STUDY OUTCOME MEASURES

Primary outcomes

- Change in HbA1C from baseline to 12 months

Secondary outcomes

Change from baseline to 12 months for:

- Rate of remission of T2DM
- Number of glucose-lowering medications
- Body weight
- Arterial blood pressure
- Lipid profile
- Adverse events (including surgical complications, hypoglycaemia and micronutrient deficiencies)
- Rate of intestinal absorption of ingested glucose (mechanistic study only)

4. PARTICIPANT ENTRY**4.1 PRE-REGISTRATION EVALUATIONS**

Screening will be performed to confirm that patients meet the inclusion criteria for the trial and are safe to undergo treatment for obesity following psychological and dietetic assessments which are part of standard care. Participants will also be invited to take part in the nested mechanistic sub-study (Appendix 2).

4.2 INCLUSION CRITERIA

- Diagnosis of T2DM
- BMI >30 kg/m²
- Age 18-65 years
- Eligible for metabolic/bariatric surgery as per NICE CG189

4.3 EXCLUSION CRITERIA

- Unacceptably high risk for anaesthesia or surgery
- Pregnancy/breastfeeding

calculated common channel length of <2.5m

4.4 WITHDRAWAL CRITERIA

All participants are free to withdraw at any time from the protocol treatment without giving reasons and without prejudicing further treatment. Should they wish to withdraw their consent, all of their data to date will be held.

5. ADVERSE EVENTS**5.1 DEFINITIONS**

Adverse Event (AE): any untoward medical occurrence in a patient or clinical study subject.

Serious Adverse Event (SAE): any untoward and unexpected medical occurrence or effect that:

- **Results in death**
- **Is life-threatening** – refers to an event in which the subject was at risk of death at the time of the event; it does not refer to an event which hypothetically might have caused death if it were more severe
- **Requires hospitalisation, or prolongation of existing inpatients' hospitalisation**
- **Results in persistent or significant disability or incapacity**
- **Is a congenital anomaly or birth defect**

Medical judgement should be exercised in deciding whether an AE is serious in other situations. Important AEs that are not immediately life-threatening or do not result in death or hospitalisation but may jeopardise the subject or may require intervention to prevent one of the other outcomes listed in the definition above, should also be considered serious.

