5.3 REPORTING PROCEDURES

All adverse events should be reported. Depending on the nature of the event the reporting procedures below should be followed. Any questions concerning adverse event reporting should be directed to the Chief Investigator in the first instance.

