5.3.1 Non serious AEs

All such events, whether expected or not, should be recorded.

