5.3.2 Serious AEs

An SAE form should be completed and faxed to the Chief Investigator within 24 hours. However, relapse and death due to causes unrelated to the trial interventions, and hospitalisations for elective treatment of a pre-existing condition do not need reporting as SAEs.

All SAEs should be reported to the London-Dulwich Research Ethics Committee where in the opinion of the Chief Investigator, the event was:

- 'related', ie resulted from the administration of any of the research procedures; and
- 'unexpected', ie an event that is not listed in the protocol as an expected occurrence

Reports of related and unexpected SAEs should be submitted within 15 days of the Chief Investigator becoming aware of the event, using the NRES SAE form for non-IMP studies. The Chief Investigator must also notify the Sponsor of all SAEs.

Local investigators should report any SAEs as required by their Local Research Ethics Committee, Sponsor and/or Research & Development Office.

Pregnancy

We ask female participants to use adequate contraception for the duration of the study. Women using the oral contraceptive pill (OCP) will be asked to stop it one month pre- and post-operatively (due to the deep vein thrombosis risk) and use alternative non-hormonal contraception which includes:

- Barrier methods
- intrauterine device (non-hormone releasing)
- vasectomised partner: this is a highly effective birth control method provided that partner is the sole sexual partner of the trial participant and that the vasectomised partner has received medical assessment of the surgical success.
- sexual abstinence: sexual abstinence is considered a highly effective method only if defined as refraining from heterosexual intercourse during the entire period of risk associated with the study treatments and when this is in line with the preferred and usual lifestyle of the subject. Periodic abstinence (e.g., calendar, ovulation, symptothermal, post-ovulation methods), declaration of abstinence for the duration of a trial, and withdrawal are not acceptable methods of contraception.

One month following surgery they can resume the OCP but there may be a chance of unplanned pregnancy which is not recommended for the first 18 months. This is due to the theoretical risk of malabsorption after RYGB. For this reason, we recommend using alternative contraceptive methods (above).

Contact details for reporting SAEs

[contact]

[name]

[contact], attention [name]

Please send SAE forms to:

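### The SAE definition requires unexpectedness and unrelated deaths are exempt from SAE reporting, so SAE counts and sponsor notification would be incomplete, although the events remain reportable as AEs

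*Protocol*

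**What the plan says.** Protocol section 5.1 begins the definition with "Serious Adverse Event (SAE): any untoward and unexpected medical occurrence or effect that" and then lists the seriousness criteria, death first. Its closing paragraph adds a judgement route, "Medical judgement should be exercised in deciding whether an AE is serious in other situations", with no condition about expectedness. The definition of an adverse event in the same section has no such condition either.

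Section 5.3 states "All adverse events should be reported" and points to two procedures. For non-serious events (5.3.1) the rule is "All such events, whether expected or not, should be recorded". For serious events (5.3.2) a form goes to the Chief Investigator within 24 hours, but the section exempts from SAE reporting "relapse and death due to causes unrelated to the trial interventions", as well as planned admissions for a condition that was already present. SAEs go to the ethics committee if the Chief Investigator considers them both related and unexpected, the latter explained as "unexpected', ie an event that is not listed in the protocol as an expected occurrence". Section 5.3.2 also says: "The Chief Investigator must also notify the Sponsor of all SAEs".

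The safety outcome in sections 2 and 3.1 is adverse events, with surgical complications named. The hypothesis in section 1.1 is that the modified operation is as safe as the standard one and better for glycaemic control.

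**The concern.** Seriousness describes what an event did to the patient. Expectedness describes whether it was foreseen. The two serve different purposes, and section 5.3.2 keeps them apart while section 5.1 merges them. Both arms receive a form of gastric bypass, so some serious complications may well be of a known type. Read literally, section 5.1 does not make these SAEs. The death exemption adds a causality opinion before a death counts, although death is the first criterion listed.

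At stake are the 24-hour form, notice to the sponsor, and the completeness of any SAE table by arm. Section 6 allows unblinding when a surgical complication calls for it, so a judgement on expectedness or relatedness could sometimes be made by someone who knows the arm. If such judgements decide what counts as an SAE, misclassification could differ between arms.

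**Working it through.** The protocol states no SAE rate, no expected share and no safety power calculation, so there is no figure to reproduce. The check sets the rules side by side for an event that meets a listed seriousness criterion.

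| Event | Section 5.1 | Section 5.3.2 |
|---|---|---|
| Unexpected, related | SAE | Form, sponsor, ethics committee |
| Unexpected, unrelated, not fatal | SAE | Form, sponsor; not ethics committee |
| Expected, any causality | Not an SAE | Its ethics committee test presupposes that such SAEs exist; they would need form and sponsor notice only |
| Death judged unrelated | SAE if unexpected | Exempt from SAE reporting, yet the sponsor must hear of all SAEs |

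(The exemption for elective admissions for a pre-existing condition is left aside; it is not in question here.)

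Four things follow.

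1. **Row 3 is a contradiction.** If section 5.1 governs, the unexpectedness test in 5.3.2 can never exclude anything. If 5.3.2 is meant to work, section 5.1 is too narrow.
2. **Row 4 is a contradiction.** The death satisfies the first criterion in 5.1 but is exempt in 5.3.2, and the sentence on notifying the sponsor makes no exception for it.
3. **Section 5.1 is uneven within itself.** An expected event of lesser severity can be called serious under the judgement paragraph, while an expected life-threatening one fails the opening definition. The judgement paragraph concerns situations other than those listed, so it does not clearly rescue the latter.
4. **Recording as an AE survives.** An expected complication meeting a seriousness criterion is an adverse event, and section 5.3 requires all of these to be reported. The explicit rule to record regardless of expectedness stands only under the non-serious heading, so for this event the duty rests on the general sentence in 5.3.

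**Size.** With n patients in an arm, true serious-event rate p, and share s regarded as expected, the SAE count under section 5.1 is n × p × (1 − s). Neither p nor s is in the document. As an illustration only, take the planned 24 and 48 patients and the same p and s in both arms:

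- p = 5%: 24 × 0.05 = 1.2 and 48 × 0.05 = 2.4 events. With s = 0.5, 0.6 and 1.2 remain.
- p = 20%: 24 × 0.20 = 4.8 and 48 × 0.20 = 9.6 events. With s = 0.5, 2.4 and 4.8 remain.
- At either rate, s = 0 loses nothing and s = 1 loses everything.

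The result runs from no loss to total loss depending on s, so these figures do not estimate the effect. The count of all AEs is unchanged throughout.

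**The case against.** The strongest reply is that the safety comparison does not rest on SAEs. A reader might infer that expected complications and unrelated deaths vanish from the comparison of the arms. The protocol does not support that: the listed outcome is adverse events including surgical complications, the AE definition has no expectedness condition, all AEs are to be reported, and the exemption in 5.3.2 concerns only reporting as an SAE. This stands.

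Second, 5.3.2 defines an unexpected event by reference to events the protocol lists as expected. No such list appears in the text available to this review, where the numbering runs from 5.1 to 5.3 and some pages are absent. With no list, that wording would make nothing expected and the definition would exclude nothing; with one, the exclusion depends on its content. This makes the size unknown. It does not remove the contradiction, and it does not touch the death exemption.

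Three further inferences should not be drawn. Section 9 says only that a data monitoring committee will be established, so the document does not show that anything would be hidden from it. Nothing in the document says that expected complications are the ones most likely to differ by limb length. And relapse is undefined rather than meaningless: remission of diabetes is a secondary outcome, so relapse of diabetes is a natural reading.

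**Conclusion.** Wrong as written, moderate severity. Sections 5.1 and 5.3.2 contradict each other on expectedness and on death. If they are followed literally, serious events regarded as expected and deaths judged unrelated escape the 24-hour form, notification of the sponsor is lost or unclear, and SAE tables by arm are incomplete. That weakens the SAE evidence for the equal-safety part of the hypothesis, while the AE secondary outcome keeps the events.

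The conclusion rests on the literal wording of the two sections and on sites applying it. It does not depend on any assumed event rate. The HbA1c outcome and the sample size are unaffected.

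**What to change.** Reconcile the two sections.

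- In 5.1, delete the words *and unexpected* from the SAE definition.
- In 5.3.2, keep relatedness together with unexpectedness solely as the test for ethics committee reporting.
- In 5.3.2, remove unrelated deaths from the exemption, so that every death is recorded as an SAE with the causality opinion noted alongside.
- Define relapse, or remove it.

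This is a short wording amendment. The running cost is a few more SAE forms and sponsor notices, for events already reportable as AEs. The set of events sent to the ethics committee does not grow, because that test still requires both relatedness and unexpectedness.
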